Subjects may be identified before being approached by examining the weekly clinical ultrasound schedule for patients who may fit the eligibility criteria. Study team members who have authorized access to electronic medical records may preview the provider schedules and do gross eligibility screening prior to the subjects being approached.

If a potential subject is identified, a member of the clinical care team will be notified by research personnel to approach the patient to determine if the potential subject is interested in participating in the study. In order to identify potential study participants, medical records will be reviewed prior to consenting.

SUBJECT REMUNERATION AND COSTS

The subject will be paid \$200 for completing the ferumoxytol infusion and the MRI at Study Visit 1 and \$100 for completing the MRI at Study Visit 2. The maximum amount of money a subject may receive is \$300.

EARLY TERMINATION AND WITHDRAWAL

Subjects are free to withdraw from participation in the study at any time upon request.

The Principal Investigator (PI) may discontinue or withdraw a subject from the study for the following reasons at his/her discretion:

- Subject non-compliance with study requirements (e.g., study intervention non-compliance)
- If any clinical adverse event (AE), laboratory abnormality, or other medical condition or situation occurs such that continued participation in the study would not be in the best interest of the subject
- If the subject is no longer an appropriate candidate for participation
- There is evidence of progressive disease or unacceptable toxicity
- If a subject does not complete either visit within the visit window, then she will be withdrawn from study treatment. A subject will also be withdrawn from study treatment if she develops any of the exclusionary criteria during the study.

Subjects who sign the informed consent form but do not receive the study intervention will be replaced. Subjects who sign the informed consent form and receive the study intervention, then subsequently withdraw, or are withdrawn or discontinued from the study, will be replaced.

The following actions must be taken if a subject withdraws, or fails to return for a required study visit:

- The site will attempt to contact the subject and reschedule the missed visit and counsel the subject on the importance of maintaining the assigned visit schedule and ascertain if the subject wishes to and/or should continue in the study.

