- Before a subject is deemed lost to follow-up, the investigator or designee will make every effort to regain contact with the subject. These contact attempts shall be documented in the study file.
- If the subject continues to be unreachable, they will be considered to have withdrawn from the study with a primary reason of lost to follow-up.

The study team will attempt to obtain the following information from subjects following early termination or withdrawal: reason for withdrawal.

Replacement of Subjects

Up to 2 subjects may be replaced if they do not complete either the infusion or MRI at Visit 1.

To minimize loss to follow-up and missing data, the study coordinator will remind the subjects of all upcoming appointments or study tasks. Before a subject is deemed lost to follow-up, the investigator or designee will make every effort to regain contact with the subject. These contact attempts shall be documented in the study file. The coordinator will check the subject's medical record for the most up to date contact information.

FERUMOXYTOL INTERVENTION

Ferumoxytol

Feraheme® (ferumoxytol) infusion is an iron replacement product currently FDA approved for the treatment of iron deficiency anemia (IDA) in adult patients who have intolerance to oral iron or have had unsatisfactory response to oral iron, or who have chronic kidney disease (CKD). To the best of our knowledge ferumoxytol is the only intravenous iron preparation that was used to localize macrophages at the site of homing in human beings. Ferumoxytol has also been investigated as an alternative in magnetic resonance angiography (MRA) for individuals who are allergic to conventional contrast agents.

Source

All study drug will be provided free of charge by AMAG Pharmaceuticals, Inc during the treatment phase.

[figure not shown]
AMAG Pharmaceuticals, Inc will distribute investigational product to the study sites. Each shipment will include a packing slip. On delivery of the product to the site, the person in charge of product receipt will follow the instructions given in the Manual of Procedures. The contents of the shipment will then be reviewed and verified against the packing slip, and will be documented as instructed at the initiation visit.

Each site's investigational pharmacy will be responsible for procuring Feraheme.

Packaging and Labeling

See package display label below.

AMAG > will provide <17 ml in 1 vial, labeled with information on warnings, handling and storage.]

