If there is an unforeseen adverse reaction, we would use the usual and customary treatment for iron infusion-associated allergic reactions, which would be no different from response to any other allergic reaction case at the obstetric triage unit. In order to facilitate and create the utmost safety, we would pre-notify the obstetric anesthesiologist on the unit in advance of the scheduled procedure. After the patient completes intravenous iron infusion and has been monitored for at least a total of an hour and has not experienced any adverse side effects, the patient will be advised to present herself for the ferumoxytol-MRI. The coordination for this will be provided by the study coordinator assigned to the study.

The vast majority of serious allergic reactions occur within short time (10 minutes) of starting the infusion. No reactions have been reported after 30 minutes of infusion. We have arbitrarily extended observation period to one hour and no one is expected to develop allergic reactions after that time.

Patients have hemogram done routinely for clinical care at 28 weeks. We will perform a panel of iron study (serum iron and transferrin levels) two-three weeks after the day of infusion. TIBC is not useful in settings of patients having received iron infusion, hence is not included in the panel.

Concomitant Therapy

There are no prohibited concomitant medications, therapies or supplements.

STUDY VISITS AND PROCEDURES

The procedures performed at each study visit are listed in the table below.

Procedure	Screening	Visit 1	Visit 2	Visit 3	Delivery	End of Study/ Postpartum
Visit Window	28 0/7 – 34 6/7 wk GA	29 0/7 - 35 6/7 wk GA	29 3/7 - 36 4/7 wk GA	2-3 wk after ferumoxytol		Delivery + 6 wks
Informed Consent	X					
Review Eligibility Criteria	X					
Demographics	X					
Review Concomitant Medications	X	X	X		X	X
Medical History	X				X	
Vital Signs		X	X			
Ferumoxytol Administration		X				
MRI		X	X			
Biological specimen collection	X				X	
Adverse Events Review/ Assessment		X	X	X	X	X
Iron Panel				X		

Screening and Enrollment

Informed Consent

Patients who express interest in the study will be referred to study personnel, who will discuss the protocol, including all procedures that will be administered as part of this research, the risks associated with participation, and the timeline for all research visits. Any questions concerning study participation will be answered before written consent is

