obtained. Potential subjects will be encouraged to take as much time as needed to consider participation.

An informed consent for participation in the study is obtained from each eligible patient, including a consent for Fe-MRI. Patients of all ethnicities for both groups are eligible.

Screening for Eligibility

1. A subject would fill out a permission to contact form in their respective clinic and the research coordinator would call the patient.
2. The telephone script would be used to determine baseline eligibility. The coordinator may send the subject a consent form so they have time to review before the consenting visit. The phone script will also ask patients if they would allow the coordinator to review their medical records before scheduling a consenting visit.
3. A consenting visit would be set up at the Center for Perinatal Care so that the subject could meet with the coordinator to ask questions and sign the informed consent document.
4. The inclusion/exclusion criteria will be reviewed with the patient.
5. Once the patient has signed the consent form documents, she will be given a copy for her records.
6. The sensitive information will be collected by the review of medical records. General information that we can rely on the patient will be collected by oral interview, however rigorous review of medical records would be necessary before enrolling the subject into the study. Per protocol, Exclusion criteria: if a patient is using tobacco/alcohol/drugs they would be excluded from the study since these factors could alter the outcome of their pregnancy putting these patients at higher risk. A MRI screening compatibility form will be completed to make sure it is safe for the patient to have an MRI performed. This is a standard form used by UW for all imaging procedures.

Enrollment

A research subject will be defined as “enrolled” in the study when they meet the following criteria:

- The subject has been consented by study staff.
- The subject and study staff have completed all screening documentation.
- The PI has verified that the subject meets all of the inclusion criteria.
- The PI has verified that subject meets none of the exclusion criteria.
- The subject has been assigned to the protocol by study staff.
- The subject has scheduled a study visit.
- The subject has received the study intervention.

On Study/Follow-up Visits

All procedures are described in detail in the “Research Procedure Descriptions” section of the protocol.

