All recorded AEs will also be available to the ICTR DMC by completing the AE/SAE forms in OnCore. The reporting requirements are consistent with those of the HS IRB, as well as the same timeframe. Once entered into OnCore, an automatic notification of an SAE will be sent to the ICTR DMC as an automated notification.

Study Stopping Guidelines

The study will be stopped or significantly changed if at least one of the following occurs:

- More than 10% of subjects experience severe claustrophobia or severe anxiety related to the MRI procedure
- For subjects receiving ferumoxytol, the study will be stopped or significantly changed if 2 subjects have an anaphylactic reaction

Subject Stopping Guidelines

If the subject experiences any adverse events or any issues arise that may affect the subject's safety, the subject will be withdrawn from the study.

The Principal Investigator (PI) may discontinue or withdraw a subject from the study for the following reasons at his/her discretion:

- If any clinical adverse event (AE), laboratory abnormality, or other medical condition or situation occurs such that continued participation in the study would not be in the best interest of the subject
- There is evidence of progressive disease or unacceptable toxicity

BIBLIOGRAPHY

4. Catalano P, deMouzon SH. Maternal obesity and metabolic risk to the offspring: why lifestyle interventions may have not achieved the desired outcomes. *Int J Obes (Lond)*. 2015;39(4):642-9. doi: 10.1038/ijo.2015.15. PubMed PMID: 25777180.

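### The withdrawal and replacement rules contradict each other and do not say that an infused woman withdrawn for an adverse event stays in safety follow-up

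*Combined protocol and SAP*

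**What the plan says.** All references are to the combined protocol and SAP.

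**Withdrawal.** Subject Stopping Guidelines state that if a subject "experiences any adverse events or any issues arise that may affect the subject's safety, the subject will be withdrawn from the study". The next paragraph of that section, like Early Termination and Withdrawal, says instead that the investigator may withdraw a subject for an adverse event at his or her discretion. Both lists of discretionary reasons include this one: "There is evidence of progressive disease or unacceptable toxicity". For a visit not completed within its window, Early Termination and Withdrawal uses a narrower term: "then she will be withdrawn from study treatment". It uses the same term for a newly arising exclusion criterion. The term is not defined, although the only drug given is a single infusion.

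**Replacement.** Early Termination and Withdrawal replaces consented women who are never infused. It also replaces women who consent and "receive the study intervention, then subsequently withdraw, or are withdrawn or discontinued from the study, will be replaced". Replacement of Subjects says: "Up to 2 subjects may be replaced if they do not complete either the infusion or MRI at Visit 1".

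**After withdrawal.** The rule written for this case is: "The study team will attempt to obtain the following information from subjects following early termination or withdrawal: reason for withdrawal". The general safety sections are wider. The Data and Safety Monitoring Plan promises monitoring of women who receive ferumoxytol and documentation of pregnancy outcome. Adverse Events of Special Interest collects maternal and neonatal events from consent to 6 weeks after delivery. Neither mentions women who have been withdrawn or replaced.

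**The concern.** Taken as written, the rules can remove an infused pregnant woman from the study because she was harmed or got worse, and then replace her. If staff treat withdrawal as the end of data collection apart from the reason, the missing delivery, neonatal and 6-week data will be related to harm or severity. That is the least tolerable kind of missing data here, because the Study Drug section itself says that existing data on ferumoxytol in pregnancy cannot inform developmental risk. Impact on the Fetus also relies on monitoring iron status, which is done at Visit 3, after the point at which a reaction would lead to withdrawal.

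The two replacement rules also give different numbers of women exposed to the drug. In addition, Study Stopping Guidelines contain one percentage rule (more than 10% of subjects with severe claustrophobia or anxiety from the MRI) and do not say whether replaced women count in it.

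**Working it through.** **1. The replacement rules, case by case**

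| Situation | Early Termination and Withdrawal | Replacement of Subjects |
|---|---|---|
| Consented, never infused | Replaced, no limit | Replaceable, within the cap of 2 |
| Infused, Visit 1 MRI not completed, withdrawn | Replaced, no limit | Replaceable, within the cap of 2 |
| Infused, Visit 1 completed, withdrawn later | Replaced, no limit | No provision |

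The first rule is mandatory and the second permissive. They part at the third Visit 1 failure, or at the first withdrawal after a completed Visit 1. The planned total is 20, and the only arithmetic behind it is 60 approached × 1/3 = 20. The second rule allows at most 20 + 2 = 22 infused women. The first has no maximum.

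**2. What is still to come for a woman withdrawn at Visit 1**

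In the Study Visits and Procedures table, the row "Adverse Events Review/ Assessment" is marked at Visit 1, Visit 2, Visit 3, delivery and postpartum, which makes 5 reviews. After Visit 1, 5 − 1 = 4 remain. The iron panel at Visit 3 also remains. The withdrawal rules do not say what happens to any of these.

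**3. The 10% rule**

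- At 20 subjects: 2/20 = 10.0% is not more than 10%; 3/20 = 15.0% is.
- At 22 subjects: 2/22 = 9.1% is not; 3/22 = 13.6% is.

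So three events meet the rule at either total, provided that all infused women count.

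A hypothetical case shows where the silence matters. The MRI section lets a woman stop the scan for claustrophobia, and an incomplete Visit 1 MRI makes her replaceable. Suppose 3 women have severe claustrophobia and 2 of them stop the Visit 1 scan and are replaced. Counting everyone infused gives 3/22 = 13.6%, and the rule is met. Counting only the final 20 gives 1/20 = 5.0%, and it is not. These counts are assumed, and the rule is taken as applied once, at the end. The plan does not say when it is applied. During accrual, 1 of the first 9 (11.1%) or 2 of the first 19 (10.5%) would already exceed 10%.

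**4. What cannot be computed**

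The documents give no withdrawal rate, so neither the chance nor the expected amount of lost follow-up can be derived.

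**The case against.** The best defence is that follow-up is already covered. The adverse-event window runs from consent to 6 weeks after delivery with no exception for withdrawal. The monitoring plan speaks of women who receive the infusion, also without exception, and events may be followed for up to a year. The item sought after withdrawal is one asked of the woman herself, whereas delivery, neonatal and pathology data come from the medical record. The site must also try to contact a woman who withdraws or misses a visit and ask whether she wishes to continue. The consent form, which was not available for this review, may settle the matter. Finally, the study is exploratory, with no test or precision target that a different replacement total would upset.

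Much of this stands, and it rules out several stronger readings that a reader might infer:

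- *That the plan abandons withdrawn women.* The general safety sections can fairly be read as covering them. What is missing is a sentence in the withdrawal rules that says so.
- *That the reaction itself goes unrecorded.* Adverse events are reviewed during the infusion and reported promptly, and acquired images are stored.
- *That replaced women drop out of the 10% rule.* No sentence says this. The Enrollment criterion "The subject has received the study intervention" points towards counting every infused woman.
- *That the drug-safety stopping rule is distorted.* The anaphylaxis rule is a count of 2 subjects and needs no denominator.

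The defence does not remove the two contradictions, on replacement and on mandatory versus discretionary withdrawal. Nor does it give staff an instruction for the woman who has been withdrawn.

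**Conclusion.** The concern holds in a limited form. The replacement rules conflict outright. The rule on withdrawal for adverse events is mandatory in one paragraph and discretionary in the next. The withdrawal rules are silent on continued safety follow-up and name only the reason for leaving, so they can be followed in a way that loses data because of harm. Such loss is permitted rather than certain.

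For a woman withdrawn at Visit 1, what is at risk is 4 of 5 adverse-event reviews and the iron panel. The total infused is at most 22 under one replacement rule and unlimited under the other. The denominator of the 10% rule is a point to clarify, and the 13.6% versus 5.0% contrast is only a hypothetical. The conclusion rests on the protocol text alone and assumes that the consent form does not already fix what happens after withdrawal. This should be fixed, because the gap concerns pregnant women given an investigational contrast agent and the remedy is cheap.

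**What to change.** 1. In Early Termination and Withdrawal and in Subject Stopping Guidelines, state that an adverse event or worsening stops the remaining study procedures (infusion, MRI) at the investigator's judgement and does not end participation. This keeps the freedom to cancel a scan for safety.
2. State that, unless she withdraws consent, every woman who received any ferumoxytol, replaced or not, stays in the planned chart review, pregnancy-outcome and telephone follow-up to 6 weeks after delivery, and is offered the Visit 3 iron panel.
3. State that she counts in all safety reporting, including the 10% claustrophobia and anxiety rule.
4. Use one replacement rule in both places. Which one is for the sponsor to choose.
5. Report the numbers infused, withdrawn and replaced.

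The cost is protocol wording, slightly more chart review, and a check that the consent form covers record review and the call after procedures stop. The chart review, postpartum call and iron panel are already planned.

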3. Placental cause: The vast majority of FGR cases of placental origin are secondary to reduced uteroplacental flow and perfusion, are generally diagnosed after 26 weeks gestation and have a high likelihood of placental lesions. This is especially true in settings of underlying vascular dysfunction (preexisting hypertension).

From the clinical point of view, the ability to detect placental malperfusion and to determine the presence of activated macrophages in the decidua basalis would help clinicians to identify the initiation of the disease pathway. This would allow us to confirm

that the pathological state has resulted secondary to reduced uteroplacental perfusion that led to FGR and to be able to detect placental etiology of FGR by visualization of placental lesions will be a substantial progress in the field.

We are requesting IRB approval for FGR sub-project in which we propose to perform contrast MRI with ferumoxytol for flow and perfusion and BOLDT similar to one proposed in the main study and to perform a follow-up MRI after the contrast agent has cleared and ferumoxytol has been picked up by macrophages.

Preliminary data: *Non-human primate (NHP) model*

In year 2, the MR sequences including the ferumoxytol approach were validated in a longitudinal primate study (n=9) throughout gestation, to establish the sensitivity, feasibility, and general safety of imaging in the first trimester for future consideration in humans. We established a non-human primate (NHP) model that will allow us to address safety concerns and guide the further conduct of human studies. We have extensively characterized the histological distribution, phenotype, and function ⁴⁸ of leukocytes in the macaque decidua and have shown in early pregnancy the dramatic influx of (primarily, innate) immune cells to the maternal-fetal interface ^{27, 49-51}. We used this expertise to evaluate the primate MFI with ferumoxytol MRI, promoting immune cell homing using intraamniotic IL1 β infusion as shown by Persicce ⁵².

Currently, there is no official registry with data on ferumoxytol use in pregnant women. However, it is being studied in pregnant women. We have done preliminary studies in a non-human primate model.

STUDY OBJECTIVES AND AIMS

The overall objective of this sub-project is to develop imaging methods to diagnose placental lesions in an on-going pregnancy, detect macrophages and correlate them with placental pathology findings in patients with clinical diagnosis of FGR.

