After subjects have been enrolled, the On-Study/Follow-up visit and the procedures performed at each visit are described in detail below.

Visit 1Ferumoxytol Infusion and 1st MRI

All procedures at this visit are for research purposes only. The infusion process, including setup of infusion and subject in the triage, subject monitoring and post-infusion monitoring will be performed as part of a paid service by qualified staff at UPH-Meriter Hospital triage. The MRI will be performed by qualified and trained clinical staff as part of a paid service at the locations listed below. The study coordinator will be present during all procedures.

Patients will receive an infusion of ferumoxytol and a same day MRI within 1-2 weeks of FGR diagnosis. This visit could occur anytime between 29 0/7 - 35 6/7 weeks gestation.

All subjects will arrive at UnityPoint Health-Meriter Hospital obstetric triage unit as prescheduled for ferumoxytol infusion. In the triage unit, the nurse will obtain baseline vital signs, including maternal pulse, blood pressure, and fetal heart rate. Following this, the nurse will initiate an infusion dose of ferumoxytol (dose). The patients will be monitored at 5 to 15-minute intervals, for pulse, blood pressure, respiration, and fetal heart rate, along with an adverse event review. In an adverse effect occurs, the attending physician, anesthesiologist and triage staff would be notified. This event will be handled similarly to any other medical emergency in triage. This infusion will last 30 minutes followed by 30 minutes of monitoring. However, the overall study visit is anticipated to last 1-2 hours this is to allow enough time for the patient to check in to triage and get settled before initiating the ferumoxytol infusion.

Following the ferumoxytol infusion, the patient will receive the first 60-minute MRI at the UW Hospital, WIMR or [name] location within 1-15 hours after completion of the ferumoxytol infusion. The purpose of this MRI is for the detection of intervillous placenta blood, placental lesions and detection of macrophages at implantation site:

Visit #2: 2nd MRI

All procedures at this visit are for research purposes only. The MRI will be performed by qualified and trained clinical staff as part of a paid service at the locations listed below. The study coordinator will be present during all procedures.

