Our IND application fully describes the iron metabolism, ferumoxytol safety and iron delivery to the fetus. (see section 9. Nonclinical Toxicology). In addition, as stated in the summary of our use of ferumoxytol as a MRI contrast agent in rhesus macaques in our IND application, there was “not significant ferumoxytol being transported across the placenta and into the fetus.” (see page 8 of the IND application, “Ferumoxytol Detection Following Infusion in Rhesus Macaque Pregnancy.”

All pregnant women are anemic, so there is no risk for iron overload. Long-lasting buildup is not possible, as all iron will be cleared by maternal macrophages within a few days. We describe the study of ferumoxytol use in pregnancy in our IND application and the determination of our colleagues that ferumoxytol is cleared from the blood 24 hours post-infusion. We will only be administering a single infusion in the proposed study. We will be only selecting subjects who are not at risk for iron overload and will be monitoring their iron status. We are also only using half the recommended dose that is used to treat anemia in pregnant women.

The estimated background risk of major birth defects and miscarriage for the indicated populations is unknown. All pregnancies have a background risk of birth defect, loss, or other adverse outcomes. In the U.S. general population, the estimated background risk of major birth defect and miscarriage in clinically recognized pregnancies is 2-4% and 15-20%, respectively. Most birth defects occur during the period of embryogenesis (organogenesis), which is completed in humans at 14 weeks gestation, based on menstrual history. We plan to use ferumoxytol during the 24-28 week window, which is well beyond the period of organogenesis; hence use of ferumoxytol at indicated time is unlikely to cause birth defects in study participants. Subjects with fetal birth defects diagnosed during the first trimester or at 20 weeks are excluded from the study.

Disease-associated maternal and/or embryo/fetal risk: Untreated IDA in pregnancy is associated with adverse maternal outcomes such as post-partum anemia. Adverse

pregnancy outcomes associated with IDA include increased risk for preterm delivery and low birth weight.

Preeclampsia and FGR Risks

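### Macrophage detection is a stated purpose of the first MRI at 1-15 h, before the protocol's own 24 h blood-clearance time, and the available text names no deciding scan

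*Combined protocol and SAP*

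**What the plan says.** Dosing and Administration and the Visit 1 section carry the same two statements. The first MRI takes place "within 1-15 hours after completion of the ferumoxytol infusion", on the day of the infusion, and its purpose is given as: "The purpose of this MRI is for the detection of intervillous placenta blood, placental lesions and detection of macrophages at implantation site".

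Other parts of the protocol set a condition on macrophage imaging. The Background describes the sub-project as a contrast MRI and a plan to "perform a follow-up MRI after the contrast agent has cleared and ferumoxytol has been picked up by macrophages". The Visit #2 section repeats this: the second scan, three to five days after the first visit, looks for macrophages once the agent has cleared. The Impact on the Fetus section cites, from the IND application, "the determination of our colleagues that ferumoxytol is cleared from the blood 24 hours post-infusion". It also says that "all iron will be cleared by maternal macrophages within a few days"; that describes the handling of iron by macrophages and does not shorten the blood figure.

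The part on interpretation and disclosure of MRI results, just before Data Collection, Handling, and Record Keeping, makes macrophage status at the implantation site the main result told to the woman. That part and the section on potential direct benefits attach suggested changes in monitoring to a positive finding. Statistical Considerations plans only to correlate MRI findings with placental pathology in 20 women.

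**The concern.** By its own reasoning, the protocol looks for macrophages after the agent has left the blood, because only then does remaining signal point to uptake by cells. The implantation site lies against intervillous blood. If agent is still circulating when that site is read, R2* or QSM signal there may come from blood, from macrophages, or from both. A macrophage reading on the first scan could then be a false positive.

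Two things make this matter in a small exploratory study. First, the reading is disclosed to the woman, entered in her record and linked to suggested changes in care, so a wrong call has consequences beyond the analysis. Second, with 20 women and one correlation with pathology, avoidable measurement variation is costly. A window 14 hours wide lets the amount of agent in blood depend on the appointment time. Any quantitative first-scan signal would carry that variation into the correlation unless the interval is known and used.

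**Working it through.** There is no sample-size, power or error-rate calculation here to reproduce. The 24-hour figure is stated without a half-life, so it can be used but not re-derived.

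**Step 1: timing.** Inputs: scan start 1 to 15 h after the infusion ends, scan length about 60 minutes (Visit 1), blood clearance at 24 h (Impact on the Fetus), second visit 3 to 5 days later (Visit #2).

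- Window width: 15 - 1 = 14 h.
- Latest scan end: 15 + 1 = 16 h.
- Gap to stated clearance: 24 - 16 = 8 h.
- Second scan: 3 × 24 = 72 h to 5 × 24 = 120 h, well after clearance.

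No permitted first scan meets the protocol's condition for macrophage imaging. Every permitted second scan does.

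**Step 2: can the two signal sources be separated?** Specific Aim 1 names R2* and QSM as the ways to detect ferumoxytol signal. It gives no rule for telling agent in blood from agent in macrophages. The visit table has MRI only at Visits 1 and 2, so there is no pre-infusion scan to subtract. The available text does not assign the first scan the role of a blood-phase reference.

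**Step 3: how far could blood level vary across the window?** The documents give no half-life, so these are assumptions chosen to agree with clearance by 24 h.

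- Linear decline to zero at 24 h: C(1)/C(15) = (24 - 1)/(24 - 15) = 23/9 = 2.6.
- First-order decline with fraction r left at 24 h: C(t)/C(0) = r^(t/24), so C(1)/C(15) = r^(-14/24).
- If same-day scheduling confines scans to an assumed 1 to 8 h: 23/16 = 1.4 (linear), or r^(-7/24).

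| Assumed decline | Left at 1 h | Left at 15 h | Ratio, 1 h to 15 h | Ratio, 1 h to 8 h |
|---|---|---|---|---|
| Linear to zero | 96% | 38% | 2.6 | 1.4 |
| 10% left at 24 h (half-life 7.2 h) | 91% | 24% | 3.8 | 2.0 |
| 5% left (5.6 h) | 88% | 15% | 5.7 | 2.4 |
| 1% left (3.6 h) | 83% | 6% | 14.7 | 3.8 |

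Slower clearance would narrow the spread, to 2^(14/10) = 2.6 for a half-life of 10 h and 2^(14/24) = 1.5 for 24 h. Those half-lives leave 19% and 50% at 24 h, which contradicts the stated clearance and puts more agent in blood during the first scan. These are ratios of concentration. How R2* or QSM scales with concentration is a further assumption.

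**Step 4: the same-day rule.** A start at 15 h falls on the same calendar day only if the infusion ends by 24:00 - 15 h = 09:00.

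**The case against.** The strongest reply is that the plan already contains the answer. Visit 2 is a dedicated post-clearance scan, and the investigator counsels the woman within two weeks of the last scan, so the later reading should normally be in hand by then. Final interpretation rests with designated readers, and nothing says that they would let the first scan override the second. In an exploratory imaging study, reading both time points is defensible, and the early scan could serve as a blood-phase comparison. This stands and limits the likely harm. It does not settle which scan decides, what happens when the two disagree, or what is reported for a woman who has only the first.

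Several stronger readings are tempting and are not supported:

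- A reader might infer that the protocol itself says the agent is in blood at 1 to 15 h. It says only that "ferumoxytol is cleared from the blood 24 hours post-infusion"; earlier presence is a sound inference.
- A reader might infer that blood signal cannot be told from uptake. The documents give no discrimination limits; the available text simply offers no method.
- A reader might infer that first scans cannot be compared between women. The spread depends on assumed kinetics and matters for quantitative signal more than for a present-or-absent lesion reading. Statistical Considerations specifies no between-women comparison of absolute first-scan signal.
- A reader might infer that the same-day rule and the 15-hour limit contradict each other. Both can be met; the first narrows the second.
- A reader might infer that no reading rule exists. The interpretation part begins mid-sentence in the text available, and the purpose sentence ends in a colon with nothing after it. A rule or list may have stood there.

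**Conclusion.** The inconsistency holds on the protocol's own words and timings: macrophage detection is a purpose of a scan that ends by about 16 h, while macrophage imaging is elsewhere reserved for after clearance, stated as 24 h for blood. The shortfall is at least about 8 h for every permitted first scan. That needs no assumption beyond a scan of about 60 minutes. It follows that a first-scan macrophage reading risks a false positive and that the available text does not keep such a reading out of the analysis or the disclosure. It does not follow that the macrophage aim is lost or that women would be misinformed, because the Visit 2 scan is suited to the purpose and comes before the usual counselling.

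The timing spread is a secondary point that rests on assumed kinetics: about 2.6- to 15-fold in blood concentration across the full window, or about 1.4- to 3.8-fold if scans fall within an assumed 1 to 8 h. That justifies recording the interval and accounting for it. It does not show that first scans are unusable, and it does not establish that any particular scan slot is needed.

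**What to change.** - Reconcile the purpose of the first MRI in Dosing and Administration and in Visit 1 with the Background, the Visit #2 section and the 24-hour statement in Impact on the Fetus.
- Define macrophage status, for analysis and for disclosure, from the Visit 2 scan only. Label any Visit 1 macrophage reading exploratory, for example as a blood-phase comparison.
- Record clock times for the end of infusion and the start of the scan for each woman. Primary Source Documents now asks only for dates.
- Show quantitative Visit 1 signal against the infusion-to-scan interval, or adjust for the interval. With 20 women, a plot is the minimum.
- State how the same-day rule and the 1-15 h window apply together. No particular slot is proposed; that choice is the sponsor's.

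The cost is a few sentences of protocol text and two recorded times per woman, with no added visit or scan. The real downside is that a woman who misses Visit 2 would have no macrophage status, because her first-scan reading would no longer count on its own. Such women should be reported as missing for this finding.
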